## **Privacy, Confidentiality, and Information Security**

### **1. Lists of Data Reviewed and/or Collected for Screening/Recruitment and Conduction of Study:**

The Personal Health Information that will be obtained, used, and/or shared for this study includes:

Identifier(s)	Source(s) of Health Information
 Names	 Medical history & physical exam information
 All geographic subdivisions smaller than a State, including street address, city, county, precinct, and zip code. Describe: VAMC/CBOC location	 Photographs, videotapes, audiotapes, or digital or other images
 All elements of dates (except year) for dates directly related to an individual, including birth date, admission date, discharge date, visit or treatment dates, etc.; and all ages over 89, Describe: fracture date, prescription fill dates, birth date, DXA testing date, death date	 Biologic specimens (e.g., blood, tissue, urine, saliva). Describe:
 Telephone numbers	 Progress notes
 Fax numbers	 Diagnostic / Laboratory test results
 Electronic mail addresses (staff only)	 Operative reports
 Social Security Numbers	 Imaging (x-ray, CT, MRI, etc.)
 Medical record numbers	 Discharge summaries
 Health plan beneficiary numbers	 Survey / Questionnaire responses
 Account numbers	 Billing records
 Certificate and/or license numbers	 HIV testing or infection records
 Vehicle identifiers and serial numbers, including license plate numbers	 Sickle cell anemia information
 Device identifiers and serial numbers	 Alcoholism or alcohol use information
 Web Universal Resource Locators (URLs)	 Drug abuse information
 Internet Protocol (IP) address numbers	 Mental health (not psychotherapy) notes
 Biometric identifiers, including finger & voice prints	 Psychological test results
 Full-face photographic images and any comparable images	 Genetic testing
 Any other unique identifying number,	 Other, describe:

Identifier(s)	Source(s) of Health Information
linked study ID, characteristic, or code, describe: A unique study ID to link patient direct identifiers, maintained in a separate file, to the other study data.	

## 2. Data and/or Specimen Acquisition:

Data for this study will be collected through:

Prospective data and/or specimen collection obtained from participants. Provide description of processes:

Prospective data collection is **for consented staff only**. The Nominal Group Technique combines quantitative and qualitative data collected from small groups of 8–20 people to rapidly generate a prioritized list of responses to specific questions during a 45–60 minute facilitated meeting. Purposive sampling will be used to include at least 2 representatives from different PACTs assigned to each of the 3 interventions for an estimated 10 sessions including at least 1 provider from all 36 PACTs. The nominal group technique will include four steps: (1) each participant writes responses to specific questions posed by the facilitator; (2) responses are anonymously recorded in a round-robin fashion, with brief discussion for clarification if needed; (3) similar responses are grouped into themes through group discussion; (4) each person records the 5 most important themes identified in step 3, in order of importance to that individual. Questions will elicit providers' perceived barriers and facilitators to osteoporosis care, experience with their assigned model, and estimated time spent per month. See grant Appendix 2 for the nominal group protocol.

Beginning in year 4, Veterans will be randomly selected to complete a bone density scan. Study staff will collect information from the medical record and scan results.

Retrospective data collection and/or specimens obtained from medical chart review/data access. Describe how data will be obtained (e.g., fileman, CDW, etc.): **For Veterans within enrolled PACT teams only**. Data is obtained through CDW queries (SQL) and manual abstraction from CPRS. At the completion of data collection, a limited dataset with direct identifiers removed will be created, and a cross-walk file maintained in a separate location. Data will not be fully de-identified.

Retrospective data collection and/or specimens obtained from an IRB-approved data and/or specimen repository. Indicate the repository source including name, VA location, and IRB number: .

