## Design

Pragmatic group randomized trial of PACT teams (n=39 teams recruited, estimated 24 at DVAHS and 15 at Richmond VAMC) will be randomized into 2 groups: a control group (no additional support, and a centralized Bone Health Service (BHS) model. Outcomes for all patients eligible for osteoporosis screening within the randomized PACTs will be assessed by investigators masked to group assignment via EHR at baseline and 2 years. Outcomes for PACT providers will be assessed using qualitative methods (nominal group technique).

**Outcome measures** are listed in the table 1 below.

Table 1. Outcome measures by Aim. RDW=Regional Data Warehouse; MPR=Medication Possession Ratio; FRAX=Fracture Risk Assessment Tool.

Outcome	Definition/Measure	Data Source/Timing	Important Difference
Patient (Panel) Level (Aim 1)			
Screening Rates	Proportion of eligible men screened in last 12 months	RDW at baseline, year 1 and year 2	25% increase from 6% Control
Medication Initiation	Proportion of screened men meeting treatment threshold (T score $\leq -2.5$ or FRAX score high-risk) who receive at least 1 prescription	RDW, intervention period year 1 and year 2, non-VA medication lists by chart abstraction.	30% increase from 55% Control
Medication Implementation	Days of medication dispensed divided by follow-up days	Pharmacy dispensing records, for patients started within prior year at baseline, year 1 and 2. Non-VA medication lists by chart abstraction.	20% increase in MPR $>80\%^{14}$ from 30% Control
Medication Discontinuation	Time between first prescription dispensing date and the date of first medication possession gap of $\geq 3$ months	Pharmacy dispensing records, for patients started within prior year at baseline, year 1 and 2. Non-VA medication lists by chart abstraction.	20% difference
Bone Mineral Density	BMD g/cm  at femoral neck and lumbar spine in random sample of men eligible for screening	Random sample of 712 men (356 UC, 178 each of the other 2 models) eligible for screening in panel at least 1 year, measured 2 years after start date	Post-intervention between group difference of 3% femoral neck, 5% lumbar spine 
Harms	Proportion of men started on oral medication for new GI distress in 3 months  Subtrochanteric fractures or Osteonecrosis of the jaw	RDW ICD10 codes, new prescription for proton pump inhibitor or H2 blocker.  RDW ICD10 codes	15% increase from 30% Control  >expected 1/50,000 patient years treatment

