## Selection of Subjects

PACT Providers (n=78, estimated 48 at DVAHS and 30 at RVAMC) include the medical provider (MD or advanced practice provider, APP) and registered nurse (RN) who provide primary care to a panel of 60 or more eligible male Veterans for osteoporosis screening. If the PACT does not have an RN assigned to the team, the PACT provider may participate alone. Providers will be identified by the ACOS and ACNS for Ambulatory Care at each site. Eligible PACT medical and RN providers must be:

- Completed training (i.e., PACT teams led by residents and fellows are excluded, unless supervised by faculty physicians)

- Care for male Veterans  $\geq 65$  years (i.e., Women's Health PACTs are excluded)

Patients (estimated n at both sites = 2376; 1462 at DVAHS) include men aged 65-85 years eligible for primary osteoporosis screening within enrolled PACT teams. Patients will be identified using Corporate Data Warehouse queries. Inclusion criteria:

- No prior fracture or osteoporosis diagnosis
- At least 1 VA Undersecretary Guideline risk factor (weight loss  $>20\%$  in 5 years; BMI  $<25$  kg/m $^2$ ; diabetes; pernicious anemia; gastrectomy; anticonvulsants; glucocorticoids; androgen deprivation therapy; hyperthyroidism; hyperparathyroidism; rheumatoid arthritis; alcohol dependence; chronic lung disease; chronic liver disease; stroke; Parkinsonism; prostate cancer; and current smoking).

Exclusion criteria:

- Active non-skin cancer diagnosis
- Enrollment in hospice or palliative care

Patients (year 4/5 sub-sample) (estimated n at both sites =900) include men aged 65-85 years, enrolled in eligible PACT team for at least 2 years, who met 1 or more criteria for osteoporosis screening as the protocol at PACT enrollment.

Exclusion criteria:

- Dual Energy X-ray Absorptiometry measurement  $<18$  months prior to outcome measurement period (minimum time required to detect a difference in BMD)
- Active non-skin cancer diagnosis
- Receiving hospice or palliative care
- Lacks capacity to provide informed consent (missing two items on the Evaluation to Consent Measure)
- Inability to transfer independently to DXA table (over scanner weight limit, spinal cord injury, bilateral lower extremity amputation)

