## Subject Recruitment

The intervention is focused on the PACT medical and RN providers; therefore, both will be asked to provide verbal informed consent for participation in all training and data collection activities. Study procedures will be described to PACT providers during a monthly Ambulatory Care meeting, with written study informational materials distributed via VA Outlook email. During the meeting participant may be given low-valued promotional items. Study personnel will follow-up individually with each provider to answer questions and complete the informed consent process. Both the PACT provider and RN must agree to participate. As PACT providers turnover in our health system, patient panels are left intact and a new provider assigned; study team members will therefore approach the new provider to request continued participation in the group randomized.

In year 3, a sub-sample of medical providers and RNs whose PACTs have participated in the care models will be recruited for a 1-hour Nominal Group session to collect qualitative data about their experience with the care model. Study staff will send out an informational Outlook email to the work address of all participating PACT providers. Those expressing interest will be contacted individually to provide more information and schedule their participation in the session. Written informed consent will be complete at the beginning of the session, as described below.

In year 4, an additional sub-sample of patients will be recruited to complete a DXA scan. Subjects will be contacted for participation in this outcome measurement regardless of whether or not they were screened during the study period; however, those screened  $<18$  months prior to the outcome assessment will be excluded since the minimum recommended time between DXA scans is 18 months. Study staff will schedule DXA at their closest VA facility. Subjects will be provided \$50 compensation for their time and travel. All subjects and their PACT providers will be provided with their DXA results for clinical decision making.

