**PACT Practice Management Model.** This model represents a robust practice management support model, with multiple tools and processes to facilitate osteoporosis care. In addition, it adds an adherence support component. All components are implemented by PACT providers, who will receive 1 hour of individualized instruction by study staff in their clinics at the beginning of the study period. The VA's COVID-19 response has increased demand on PACT providers. With input from stakeholders including PI's, statisticians and providers and the ACOS, to decrease the time burden on PACT providers assigned to this arm, the study team will re-randomize and re-consent PACT team, therefore, eliminating PACT practice management activities and analysis.

**Bone Health Service Model** – Patients in PACTs randomized to the BHS model will have osteoporosis screening, education, and follow-up handled centrally by the bone health team. PACT providers can opt out of the service for patients in whom they believe it is not appropriate, and approve all orders, but are not responsible for most activities.

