PACT satisfaction, time	Nominal Group Technique at Routine Staff meeting	Measured at 2 years	
Health System/Policy Level (Aim 3)			
Program Cost Effectiveness	Cost/quality adjusted life years (QALY) of the screening models compared to control	Markov model with above outcomes, fracture rates, cost and quality of life from VA and medical literature	Probability of cost/QALY >80% at thresholds of \$50,000, \$100,000, \$200,000 

**Provider-level Covariates** will be collected from the PACT providers at the time of randomization, including medical provider type (Advanced Practice Provider vs. MD), medical provider and RN years in practice, years in VA, and practice site (rural CBOC, urban CBOC, VAMC).

**Patient-level Covariates** will be extracted from the Regional Data Warehouse and CPRS. Demographics include age, self-reported race, body mass index, and rural zip code as classified by Rural-Urban Commuting Area. Because medication co-pays may be a barrier to adherence, co-pay status will be collected. Co-morbidities related to fracture risk include chronic lung disease, diabetes, endocrine disorder (hyperthyroidism, hyperparathyroidism, Cushing's, hypogonadism), prostate cancer, rheumatoid arthritis, Parkinson's disease, stroke, gastrectomy/malabsorption, smoking, alcohol abuse, chronic kidney disease, chronic liver disease, dementia. Medications include calcium, vitamin D, glucocorticoids, androgen deprivation therapy, traditional anti-epileptic drugs, proton pump inhibitors, selective serotonin reuptake inhibitors, and psychoactive medications.

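### The Nominal Group sampling rule still follows the dropped three-arm plan, asks for more seats than there are providers, and as best read yields no arm-specific result for H2b

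*Protocol*

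**What the plan says.** The sampling rule is in the Protocol's privacy part, section 2 (Data and/or Specimen Acquisition). It gives a group size of 8 to 20. Sampling is purposive, with at least two representatives from different PACTs "assigned to each of the 3 interventions for an estimated 10 sessions including at least 1 provider from all 36 PACTs". Participants write answers, similar answers are merged into themes by group discussion, and then "each person records the 5 most important themes identified in step 3, in order of importance to that individual". The questions cover barriers and facilitators, the provider's own assigned model, and time spent.

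Other places bear on this rule:

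- **Protocol, Design:** "n=39 teams recruited, estimated 24 at DVAHS and 15 at Richmond VAMC", and these teams "will be randomized into 2 groups". Study Interventions removes the third arm, "eliminating PACT practice management activities and analysis".
- **Protocol, Selection of Subjects:** the providers are "n=78, estimated 48 at DVAHS and 30 at RVAMC". A provider whose team has no RN may take part alone.
- **Protocol, Subject Recruitment:** "a sub-sample of medical providers and RNs whose PACTs have participated in the care models will be recruited for a 1-hour Nominal Group session". All participating providers are emailed, and those who express interest are scheduled.
- **Table 1 (Protocol and SAP, Design):** provider satisfaction and time are measured by "Nominal Group Technique at Routine Staff meeting".
- **Protocol, Risk/Benefit Assessment:** responses and ranking sheets are anonymous.
- **Protocol, Nominal Group Analysis:** scores are averaged over group members. Themes are then scored across groups and examined by site characteristics and provider type.
- **Protocol, Specific aims:** H2b predicts higher provider satisfaction in BHS PACTs than in usual care.

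**The concern.** Two matters arise. First, the sampling sentence is operative text, yet it describes a design that no longer exists and a number of sessions that the enrolled providers cannot fill at the stated group size. Study staff cannot follow it as written.

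Second, H2b is a comparison between arms, and the Nominal Group Technique is its named measure. If each session contains both arms, answers are merged before voting, the votes carry no described arm label, and the planned breakdowns do not include arm. A BHS provider and a usual-care provider would then rank the same merged list, including themes that come from the other arm's model. Aim 2 would give an overall list of themes but no result for BHS against usual care. Because the sheets are anonymous, the arms could not be separated afterwards.

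**Working it through.** **1. Team and provider counts.** Teams: 24 + 15 = 39. Providers at two per team: 39 × 2 = 78, which equals 48 + 30. The Protocol's 78 is reproduced. It is a ceiling for 39 teams, because a team without an RN contributes one person.

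**2. Origin of the stale counts.** The SAP's original power section uses 12 PACTs per group in three groups: 3 × 12 = 36. The same sampling sentence stands in the SAP's original three-arm text. The current figures are 2 groups and 39 PACTs (19 BHS, 20 usual care), so the sentence is out by one arm and 39 − 36 = 3 teams. The SAP's revised aims and revised analysis plan do not replace it.

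**3. Seats against providers.** Seats = sessions × group size, assuming each provider attends once.

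- Minimum: 10 × 8 = 80, short by 80 − 78 = 2 (2/78 = 2.6%).
- Maximum: 10 × 20 = 200, short by 200 − 78 = 122.
- If all 78 attend: 78/10 = 7.8 per session, or 9 full sessions of 8 (9 × 8 = 72).
- On the sentence's own 36 PACTs: 36 × 2 = 72 providers, short by 80 − 72 = 8.

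The documents give no participation rate and no number of teams without an RN. For the participation rate, an assumed range:

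| Assumed participation | Attendees | Sessions of 8 that can be filled |
|---|---|---|
| 100% | 78 | 9 |
| 90% | 70.2 | 8 |
| 75% | 58.5 | 7 |
| 50% | 39 | 4 |

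If 5 or 10 teams had no RN (also assumed), the ceiling would fall to 73 or 68, a mean of 7.3 or 6.8 over ten sessions.

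**4. Which reading of the sampling sentence?** As a quota over the whole sample, two representatives per intervention means 2 × 3 = 6 people. The same sentence already requires a provider from every one of 36 PACTs, which is 12 per arm under the original plan, so an overall quota of two adds nothing. The phrase does work only if it applies to each session. Read that way it needs 2 × 3 × 10 = 60 attendances for three arms, or 2 × 2 × 10 = 40 for two, and both are below 78. Two further points agree with this reading: Table 1 sets the sessions in routine staff meetings, and randomisation was blocked by site, so one clinic's meeting can hold both arms. No passage says that sessions are arm-specific.

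**5. Following H2b through the analysis.** H2b needs a result for BHS and a result for usual care. In a mixed session the described steps are anonymous written answers, themes merged by the whole group, an anonymous ranking of five merged themes, a score averaged over all members, theme scores across groups, and tables by site characteristics and provider type. Arm enters at none of these steps.

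**The case against.** The strongest reply is that mixed sessions are inferred, not stated. The sentence could describe the overall sample, or sessions held by intervention. It refers to a nominal group protocol in a grant appendix that is not among the documents and may settle the matter. Interested providers are scheduled individually, which does not require an intact clinic meeting, and small CBOCs were combined for randomisation, so a clinic need not contain both arms. All of this stands as a reason to write that mixing is the better reading, not a certainty. It does not supply the missing breakdown by arm.

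On the numbers, the minimum shortfall is two people, the session count and the site counts behind 78 are estimates, and 8 to 20 appears in a general description of the technique. This also stands. The arithmetic shows that the session count needs restating, not that the sessions will fail.

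Some stronger conclusions are tempting but unsupported:

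- A reader might infer that providers are asked to judge a model they never used. The question concerns each provider's own model, and ranking is by importance to that person. The most that follows is that, in a mixed session, a provider may rank a theme that came from another arm.
- A reader might take 19 BHS and 20 usual-care teams to mean that about half the votes on BHS themes come from outside BHS. Team counts are not vote shares, and the share is unknown.
- A reader might divide 36 or 39 PACTs by ten sessions and expect about four voters each. One provider per PACT is a floor, not an attendance target, and final themes are built across groups.
- Drawing participants from both arms is not itself a fault. H2b requires it.

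**Conclusion.** The point holds in three parts of differing certainty. The mismatch of 3 interventions and 36 PACTs with 2 groups and 39 PACTs is plain on the page. The seat count exceeds the provider ceiling by at least 2 if each provider attends once. That is trivial at full participation, but it grows to a plan in which only 4 of 10 sessions can be filled at an assumed 50%. The lack of an arm-specific result for H2b is the part of consequence. It rests on reading the two-per-intervention rule as a rule for each session, which is the reading that gives the phrase any effect. Even if sessions turn out to be arm-specific, the plan should say so and name arm in the analysis.

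The effect is confined to the qualitative provider outcome in Aim 2. It does not touch the Aim 1 outcomes or their power. It is more than an editorial note because the remedy must be in place before the sessions are held.

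**What to change.** - In the Protocol's Data and/or Specimen Acquisition section, change the sampling sentence to 2 groups and 39 PACTs.
- Restate the number of sessions as the expected attendance divided by a group size of at least 8, and give the expected attendance. The documents do not support one fixed number.
- Run the theme list and the vote for the model-experience and satisfaction questions within arm. Where a session must mix arms, mark the anonymous ranking sheets by arm.
- In the Nominal Group Analysis, add arm to the planned breakdown, report the top themes for BHS and usual care separately, and say how these will be used to assess H2b.
- Carry the same wording into the SAP.

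The cost is wording and scheduling. Separating the arms loses little capacity: 19 × 2 = 38 BHS providers fill 4 sessions of 8 and 20 × 2 = 40 usual-care providers fill 5, so the total at full attendance is still 9. At 75% each arm (28.5 and 30) fills 3, a total of 6 against 7 when pooled. Arm-specific sessions may not fit every routine staff meeting. In that case arm-marked sheets suffice, and they record the arm without identifying the person, so anonymity is kept.

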## 3. Level of Data:

The following level(s) of data will be acquired/maintained for this study (*check all that apply*):

- Identified (e.g., names, addresses or other identifiers included)
- Coded (direct and/or all identifiers removed, but study code/ID included)
- De-Identified (all HIPAA 18 and study ID/code removed):
  - Verified Statistically
  - OR
  - Verified by Absence or Removal of HIPAA 18 and study ID
- Limited Data Set
- Other: Describe:

#### **4. Location of Data and/or Specimens, and Data Retention Plan:**

##### A. Data and/or Specimen Location:

Data will be stored electronically in

[\\vhadurhsmcifs01.v06.med.va.gov\DHURHAM\\_HSRD\\_P\MOOPS](\\vhadurhsmcifs01.v06.med.va.gov\DHURHAM_HSRD_P\MOOPS). Data that will be stored electronically are listed in the “Outcome Measures” and “Covariates” sections, and summary results from provider nominal group techniques.

Paper records of data include staff demographic surveys. They will be stored in a locked cabinet in the DVAHS Geriatrics Research Education and Clinical Center (GRECC) room N3006, Durham VA Hospital.

There are no biological specimens.

- Data will be also be placed at the VA Informatics and Computing Interface (VINCI; <http://vaww.vinci.med.va.gov/vincicentral/VINCIWorkspace.aspx>). The VA Informatics and Computing Infrastructure is a partnership between the VA Office of Information Technology and the Veterans’ Health Administration Office of Research and Development. Researchers and operations staff can use VINCI to access data and statistical analysis tools in a virtual working environment through a certified VHA network computer using the VA Intranet or Virtual Private Network (VPN).

